Account, member, certificate or professional license numbers, health beneficiary numbers		

Vehicle identifiers and serial numbers, including license plate numbers		
Check 'None' when none of the identifiers listed above will be recorded, maintained, or shared during the conduct of this study. (exempt category 4)	 None	 None

Data Analysis

Power analyses may not be appropriate if this is a feasibility or pilot study, but end-point analysis plans are always appropriate even if only exploratory. Provide all information requested below, or provide justification if not including all of the information.

Power Statement:

Population Justification:

We have determined that healthy volunteers should be sufficient to validate the metrics of tidal volume and respiratory rate, due largely to the fact that healthy volunteers are able to breathe through a range of respiration rates and tidal volumes without putting their health at risk. Using the intended use population, who are generally ailing, struggling to breathe normally, and elderly, we would likely not be able to cover the full range of measured values with as much standardization as we would like to in this protocol. The mode of operation of the device and its use does not change whether a subject is healthy or part of our intended use population, and thus we believe that whether this data comes from healthy or ill volunteers does not matter in this case.

Sample Size Justification:

Based on prior studies data, the mean error (e.g., bias) of the respiration rate across 6 and 40 bpm ranges between -0.02 and -0.16 bpm, and the standard deviation of the error ranges between 1.74 and 3.31 bpm. To demonstrate the mean error is less than ± 1 bpm, we will use a worst-case scenario of the mean error of -0.16 bpm with a standard deviation of 3.31 bpm. For two-sided hypothesis testing with significance level ($\alpha=0.05$) and with 90% power ($\beta=10\%$), the minimum sample needed across 6-40 bpm is 202. Given that 9 readings will be collected per each participant, the minimum number of subjects is 23.

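### The respiration-rate sample size of 202 readings (23 subjects) gives about 95% power on the protocol's own inputs, so it is sufficient but is not the minimum for the stated 90%

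*Protocol*

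**What the plan says.** The Protocol, under Sample Size Justification, sets the aim of the respiration-rate calculation as "To demonstrate the mean error is less than ± 1 bpm". It takes a "worst-case scenario of the mean error of -0.16 bpm with a standard deviation of 3.31 bpm", and specifies a two-sided test at alpha 0.05 with 90% power (beta 10%). From this it concludes that "the minimum sample needed across 6-40 bpm is 202". It continues: "Given that 9 readings will be collected per each participant, the minimum number of subjects is 23". No formula or software is named.

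The next paragraph, on tidal volume, uses 95% power (beta 5%). The section then sets both minimum figures aside and plans 40 subjects, with up to 60 if necessary. The SAP, under Analysis 1, treats all data points as independent, including those from the same subject.

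**The concern.** A figure presented as the minimum for a given power should follow from the inputs beside it. Here it does not. The usual calculation at 90% power gives a clearly smaller number, and 202 appears only when the power term is the one for 95%. Without a formula, a reader cannot tell whether the power label is wrong or a more cautious method was used.

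Little is at stake for the conduct of the trial. The matter is whether the stated calculation can be traced. The Protocol says the study is meant to support a 510(k) submission, so someone checking the number from the stated inputs would arrive at a different one.

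**Working it through.** **Inputs (Protocol, Sample Size Justification).** Margin ±1 bpm; mean error -0.16 bpm; SD 3.31 bpm; two-sided alpha 0.05, so z = 1.960; power 90%; 9 readings per subject. Independence of readings is taken from SAP Analysis 1.

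The assumed mean error lies 1 - 0.16 = 0.84 bpm from the near limit (-1) and 1 + 0.16 = 1.16 bpm from the far limit (+1).

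**Step 1: reproduce 202.** The normal-approximation formula for showing that a mean lies inside a limit is

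n = (z_alpha + z_power)² × SD² / distance².

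| z_alpha | z_power | Distance | n | Rounded up |
|---|---|---|---|---|
| 1.960 | 1.645 | 0.84 | 201.8 | **202** |
| 1.960 | 1.282 | 0.84 | 163.2 | 164 |
| 1.645 | 1.282 | 0.84 | 133.0 | 133 |
| 1.645 | 1.645 | 0.84 | 168.0 | 169 |
| 1.960 | 1.282 | 1.00 (no bias) | 115.1 | 116 |
| 1.960 | 1.645 | 1.00 (no bias) | 142.4 | 143 |

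First row written out: (1.960 + 1.645)² × 3.31² / 0.84² = 12.996 × 10.956 / 0.7056 = 201.8. Of the variants tried, only this one gives 202. Then 202 / 9 = 22.4, so 23 subjects, as stated.

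The quantile 1.645 is z(0.95). It arises in two ways: from beta/2 = 5% at each limit, or from a 95% power target.

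**Step 2: power actually achieved.** With SE = 3.31/√n and both limits counted,

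power = Φ(0.84/SE - 1.960) + Φ(1.16/SE - 1.960) - 1.

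At n = 202, SE = 0.2329. The first term is Φ(1.647) = 0.9502 and the second is Φ(3.021) = 0.9987, so power is 94.9%. The chance of missing is about 5.0% at the near limit and 0.1% at the far limit.

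| Readings | Power, normal | Power, t-based |
|---|---|---|
| 164 | 89.6% | 89.2% |
| 166 | 89.95% | 89.6% |
| 167 | 90.1% | 89.8% |
| 169 | 90.5% | 90.2% |
| 202 | 94.9% | 94.7% |
| 207 (23 × 9) | 95.4% | 95.2% |
| 360 (40 × 9) | 99.8% | 99.8% |

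So 90% is first reached at 167 readings (169 with a t test). The simple near-limit formula, 164, falls just short once the far limit is counted.

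**Step 3: how firm the surplus is.** At 23 subjects the surplus is 207/167 = 1.24. With 9 readings per subject and a common within-subject correlation rho, the design effect is 1 + 8 × rho. Setting 1 + 8 × rho = 1.24 gives rho = 0.03. A correlation that small would bring power at 23 subjects back to about 90%.

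**The case against.** The strongest defence is that 202 does deliver what is claimed. Splitting beta over the two limits is exact when the true mean error is zero, and it remains a valid conservative bound at any mean error inside the margin. If the chance of missing at the nearer limit is at most 5%, it is no larger at the farther one, so the total cannot exceed 10%. The figures in Step 2 (5.0% and 0.1%) bear this out. That stands: the number is adequate, and a beta/2 method would be cautious rather than invalid. What does not survive is calling 202 the minimum for 90% power.

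It is also fair to say that nothing in the trial turns on this. Enrolment is set at 40, and the SAP's respiration-rate success rule rests on the proportion of errors within ±2 bpm (Analyses 1-2 and 1-4), not on the mean error powered here. Whether the mean error is the right quantity to power is a separate question, which this point neither raises nor settles.

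Two stronger readings are tempting. First, a reader might infer that the sponsor misapplied beta/2. The documents do not show this. No formula is given, and since the tidal-volume calculation that follows uses 95% power, a mislabelled 95% fits equally well. Second, a reader might infer that 167/9 = 18.6, hence 19 subjects, would have been enough. That holds only if nine readings from one person are independent. The SAP asserts this for the errors, and its stated support (similar mean and median errors across rate conditions) does not address correlation within a subject.

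**Conclusion.** The point holds as a minor inconsistency in the conservative direction. On the stated inputs, 202 readings give 94.9% power and 23 subjects (207 readings) give 95.4%, about 5 percentage points above the stated 90%. A true minimum for 90% would be about 167 readings (164 to 169 depending on the variant). The stated number is sufficient; it is mislabelled as the minimum for that power.

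These figures assume normally distributed, independent errors and the stated mean and SD. The mismatch between 202 and 90% is arithmetic. Its cause is inferred and cannot be settled from the documents. The study is not left short: under the same assumptions, 40 subjects (360 readings) give about 99.8% power for this hypothesis.

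**What to change.** In the Protocol's Sample Size Justification, restate the respiration-rate sentence as about 95% power for 202 readings (23 subjects at 9 readings each). The word about is needed, since 202 readings give 94.9% when both limits are counted. Add the formula with its quantiles and the 0.84 bpm distance, and state that the calculation assumes independent readings within a subject. If a conservative beta/2 split was intended, say so, so that a reader can see why the number exceeds what 90% needs.

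Do not use the surplus to argue for fewer subjects. The planned 40 (up to 60) stay as they are. The cost is one corrected sentence, with no operational effect.

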[figure not shown]

Title: SAP0002 Clinical Statistical
Analysis Plan

NCT: NCT05445206

	Name	Role / Function	Signature	Date
Prepared By	[name]	Biomedical Systems Engineer		May 11 2022
Reviewed By	[name]	Algorithm Engineer		May 11, 2022
	[name]	Biomedical Engineer, Clinical Trial		May 12, 2022

Introduction:

This document describes the statistical analysis planned for the clinical evaluation data. The study is described in the clinical evaluation protocol (CEPR0002).

Analysis Plan:

Analysis 1: Respiration rate accuracy

The primary objective of this analysis is to demonstrate whether 85% of the errors are bounded within ± 2 bpm. It is noted that we will be using 85% instead of 95% because the CPM system is intended to give a trend, represented by multiple data points over time. This means the errors in the individual data points are averaged out in the trend interpretation, therefore justifying the change from 95% to 85%.

Respiration rate under natural breathing condition, if available, and controlled breathing condition (6, 10, 15, 20, 25, 30, 35, 40 brpm) will be summarized for CPM system and clinician annotated capnography. Although multiple breathing rates conditions are achieved within a subject, each data point is considered independent from each other. Prior look-ahead testing showed that there's no difference in mean errors and median errors across different breathing rate conditions, thereby justifying analyses after pooling all rate conditions together.

The error will be calculated by the difference between the CPM system's estimate and clinician annotated reference for each body posture. The error will be summarized using descriptive statistics and its limits of agreement. If the initial clinician's annotation is strongly suggested to be inaccurate by the compelling evidence (e.g., significant deviation from the simulated breathing or equivalently strong observations), the second annotator may be introduced to read the capnography waveform independently. The final respiration rate is determined based on two annotator readings.

Analysis 1-1: Respiration rate error descriptive statistics

The descriptive statistics includes but not limited to:

- Percentage of the CPM system's RR estimate not reported due to bad signal quality.
- Mean, median, variance, standard deviation, skewness, kurtosis, root mean squared error, and root median squared error.

Analysis 1-2: Percentage of respiration rate error within ± 2 brpm

Using the data that are classified by the CPM system as good quality, the percentage of the respiration rate whose error is within ± 2 brpm is derived. The confidence interval for the proportion of the errors within ± 2 brpm will also be characterized assuming that the number of data points whose errors are within ± 2 brpm follows binomial distribution.

Analysis 1-3: Respiration rate error limits of agreement

The limits of agreement will be derived using a conventional Bland-Altman analysis as well as non-parametric approach in case the distribution of the error has a long-tail, significant deviation of Normality assumption of the conventional Bland-Altman analysis.

The 85% limits of agreement (bias \pm 1.44 standard deviation) will be tabulated. The 95% confidence interval for the limits of agreement will also be derived. In case the kurtosis, calculated in the Analysis 1-1, is high indicating that the distribution of errors has a long tail, non-parametric limits of agreement will also be presented to correctly characterize the range which 85% of the errors are expected to be bounded by. The non-parametric 85% limits of agreement will also be derived based on 7.5% and 92.5% percentile of the errors. The 95% confidence interval for non-parametric limits of agreement will be derived using a bootstrap resampling method.

Analysis 1-4: Other respiration rate accuracy analyses

A 95% confidence interval (CI) for mean error (i.e., bias) will be tabulated. While the primary objective is to show that the CPM estimate is accurate within ± 2 brpm, the CI for mean error will additionally show if there is any systemic bias in the CPM estimate. The standard deviation of the paired differences will also be tabulated.

If the lower bound of the 95% confidence interval for the percentage of the errors within ± 2 bpm from Analysis 1-2 exceeds 85%, it is demonstrated with statistical significance that the CPM system's respiration rate accuracy is sufficient in comparison to the reference to support its intended use. Also, the other analyses should provide different lenses to characterize the respiration rate accuracy.

Analysis 2: Accuracy of relative changes of relative tidal volume

The primary objective of this analysis is to demonstrate the CPM system's relative tidal volume (rTV) is accurately tracking true changes in tidal volume (TV).

For each subject, relative tidal volume from the CPM system and the tidal volume from the reference device under the breathing-depth controlled condition (natural ~ 500 mL, shallow ~ 250 mL, deep ~ 750 mL, very deep >1 L) and the breathing-rate controlled condition (e.g., 10, 15, 25, 30 bpm) will be compared for each body posture. A scatter plot of relative tidal volume produced by the CPM system and the tidal volume measured by the reference device will be produced. Each graph will be summarized by two least-squares linear regression fits. One is produced in a linear scale and the other is produced in a log scale to characterize the relative accuracy.

Analysis 2-1: Respiration rate error descriptive statistics

The descriptive statistics includes but not limited to:

- Percentage of the CPM system's rTV estimate not reported due to bad signal quality.
- Mean, median, variance, standard deviation, skewness, kurtosis, root mean squared error, and root median squared error.

Analysis 2-2: Least-squares linear regression analysis in rTV and TV

The accuracy of relative changes of rTV will be summarized by Pearson correlation coefficients across subjects. Then, mean correlations will be determined using Fisher's z-transformation to combine the subject specific coefficients and then back transformed. A 95% confidence interval on mean correlation coefficient will also be derived.

Analysis 2-3: Least-squares linear regression analysis in natural logs of rTV and TV

The accuracy of relative changes of rTV will be summarized by Pearson correlation coefficients across subjects obtained using natural logs of rTV and TV. Then, mean correlations will be determined using Fisher's z-transformation to combine the subject specific coefficients and then back transformed. A 95% confidence interval on mean correlation will also be derived.

After the linear fit, root mean square of the relative residual errors will also be characterized. A 95% confidence interval on the root mean squared relative errors will also be derived using Chi-squared distribution assuming the relative residual errors follows a zero-mean Gaussian distribution.

If the root mean square of the relative errors from Analysis 2-3 and its confidence interval does not exceed 35% per end-point in the protocol (CEPR0002), it is demonstrated that the CPM system's relative tidal volume is sufficiently accurate in following relative changes in comparison to the reference. Mean correlation coefficients from Analysis 2-2 and 2-3 will also support that the primary objective of this Analysis 2 is achieved.

Analysis 3: ECG and Skin Temperature Capabilities

The primary objective of this analysis is to evaluate the secondary objectives regarding the ECG and skin temperature capabilities of the CPM system. For skin temperature, the descriptive analyses will be performed in comparison the reference measurement For ECG capabilities, if the data is available, the quality of the CPM ECG can be evaluated.

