Upon arrival to the clinic on the day of the study visit, prior to the application of the reference and test devices, skin inspection of the application site will be conducted. The CPM Device will then be applied to the participant's chest as described in the IFU materials supplied with the device (the study team will also have received training on the proper placement of the device prior to the initiation of the study). This device will be worn for the entirety of the clinic visit (without removal and replacement). The reference device will also be used for each measurement taken during the visit, concurrently. On the CRF, the time that the CPM Device is placed on the chest will be denoted.

A Baseline measurement will then be initiated using the CPM Mobile Application in order to assign a system-generated patient ID to the participant as well as to establish the tilt angle for the following measurements. The first half of the measurement should be in the Fowler, sitting-upright position, and the second position should be in a Supine, lying-flat position. The reference device will also be used during this time to establish a respiration baseline.

The exercises below will then be followed, with the time of the start of each exercise recorded in the CRF. Four different versions of the exercises (Procedures A-D) will be available that differ only in the sequence of the measurements. The study staff will randomly select a procedure version, using the EDC. Only one procedure version per subject is used. The selected version for each subject will be recorded.

Each exercise will last approximately 4 minutes, or the time that it takes to complete one full measurement with the CPM device in measurement mode (initiated by the CPM mobile app). Within each measurement, participants will move through two positions, both upright and supine. Reference respiration data will be taken concurrently with the CPM device measurement. For each measurement, it is ensured that the reference device recordings are stabilized before initiating the CPM measurement sequence.

For items 1-17, capnography waveform and breath-by-breath reference tidal volume from a metabolic cart will be simultaneously recorded for comparison. For item 18, a diagnostic ECG and clinical grade temperature sensor data will be collected simultaneously.

<Procedure A>

Item	Respiration Rate	Tidal Volume	Mode	Duration
1	Natural (baseline)	Natural (baseline)	Doctor Setup, App	4 min

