A single metered breathing app or metronome will be used to pace respiration rates throughout the study. The same breathing pacing method will be used across all patients. It is assumed that actual respiration rates will differ slightly from those described in the protocol. Higher and lower respiration rates may be tailored slightly to accommodate the abilities of participants. During both phases of varying respiration rate (items 1-9 in above table) and varying tidal volume (items 10-17 in above table), both respiration rate and tidal volume will be tracked from the reference device.

Readings will not be considered "successful" or "complete" unless all CPM device errors are resolved prior to the device streaming mode. In the case that a contact or tilt error cannot be resolved, the measurement must be repeated until the data quality is deemed sufficient. If the device begins peeling off of the skin during a measurement (as noted by a participant or by a study staff) and the streaming data quality looks questionable, the measurement must be repeated and the adhesives replaced to ensure good contact. It is recommended that if the electrode contact issues are cumulatively encountered three times, adhesives must be replaced to restore good device attachment to the body. The IFU can be followed for troubleshooting tips regarding issues with data quality. The device may have to be replaced, the skin moisturized, or the adhesive on the device replaced. Any note regarding measurement issues and steps taken to resolve these issues must be noted in the CRF. If the above actions were not taken, the relevant readings should be excluded based on the deviation of the study protocol.

The recorded capnography waveforms, simultaneously acquired with the CPM readings for Items 1-17, will be interpreted by clinicians in a blinded fashion to provide the measured respiration rate as a reference. After time synchronization between the capnography and the CPM system, the sponsor will provide the clinicians with segments in the continuous capnography waveform corresponding to the duration of the CPM system readings. Clinician(s) will then be asked to annotate and provide the reference respiration rate.

Discontinuation/withdrawal of participants from the study:

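### The respiration-rate endpoint is decided by a binomial interval that treats up to 18 readings from one subject as independent; any correlation within subjects inflates false success

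*SAP*

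**What the plan says.** SAP Analysis 1 pools natural breathing, where available, with eight controlled rates (6 to 40 per minute) and computes an error for each posture. The protocol's Study Procedures confirm two postures per reading: "Within each measurement, participants will move through two positions, both upright and supine". The SAP recognises that readings repeat within subjects and sets this aside: "Although multiple breathing rates conditions are achieved within a subject, each data point is considered independent from each other". The support it offers is that prior testing showed "no difference in mean errors and median errors across different breathing rate conditions".

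Analysis 1-2 begins "Using the data that are classified by the CPM system as good quality" and forms the confidence interval "assuming that the number of data points whose errors are within" ±2 brpm is binomial. Analysis 1-4 makes that interval the decision rule: "If the lower bound of the 95% confidence interval for the percentage of the errors within" ±2 bpm exceeds 85%, accuracy is declared shown with statistical significance. The 85% criterion is the respiration-rate endpoint in the protocol's Endpoints section.

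Analysis 1-3 adds conventional Bland-Altman limits and non-parametric limits whose interval "will be derived using a bootstrap resampling method"; the unit to be resampled is not stated.

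**The concern.** Equal mean and median errors across breathing rates bear on whether rates may be pooled. They say nothing about whether one subject's readings tend to pass or fail together, which is what a binomial count of data points requires.

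The design gives reasons to expect that they do. Each subject attends one session with the device kept at one skin-marked position. The rate is derived from impedance across that subject's chest, and recruitment deliberately seeks a range of body types and BMIs. Both postures come from the same measurement. The SAP already works by subject elsewhere: Analyses 2-2 and 2-3 combine subject-specific correlation coefficients.

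If readings correlate, the sample carries less information than its count suggests, the lower limit is too high, and a primary claim meant to support a 510(k) submission could be called significant when the data do not support it. The intervals for the mean error and the limits of agreement would be too narrow for the same reason if computed per reading.

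**Working it through.** **1. The plan's own figure.** The protocol's Sample Size Justification uses a mean error of −0.16 bpm, SD 3.31 bpm, a margin of ±1 bpm, two-sided α 0.05 and 90% power. The stated 202 reproduces with z(1−β/2) = 1.645:

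n = [3.31 × (1.960 + 1.645) / (1 − 0.16)]² = 201.8, rounded up to 202; 202/9 = 22.4, rounded up to 23 subjects.

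This also counts readings as independent, and it sizes a test of mean error, not the 85% rule.

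**2. Cutoff under the SAP rule.** Nine conditions × 2 postures = 18 points; 40 subjects × 18 = 720. The smallest count whose lower 95% limit exceeds 0.85 is 631 (631/720 = 87.6%) with the exact or Wilson interval, and 630 with Wald. The SAP does not say which is meant.

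**3. False success at a true 85%.** The documents give no ICC, so a range is assumed. Each subject has their own pass probability, beta-distributed with mean 0.85; subject totals are beta-binomial, and the distribution of their sum over 40 subjects is exact by convolution. Between-subject SD = √(ICC × 0.85 × 0.15). Design effect = 1 + 17 × ICC. Normal approximation = 1 − Φ(1.96/√design effect).

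| ICC | SD of subjects' pass rates (points) | Design effect | Effective N | Normal approx. | Exact P(count ≥ 631) |
|---|---|---|---|---|---|
| 0 | 0 | 1.00 | 720 | 2.5% | 2.5% |
| 0.02 | 5 | 1.34 | 537 | 4.5% | 4.4% |
| 0.05 | 8 | 1.85 | 389 | 7.5% | 7.4% |
| 0.10 | 11 | 2.70 | 267 | 11.6% | 11.7% |
| 0.20 | 16 | 4.40 | 164 | 17.5% | 18.1% |

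A probit random-intercept model gives 4.3%, 7.2%, 11.7% and 18.0% at ICC 0.02 to 0.20.

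**4. Other numbers of points and subjects** (exact binomial rule, true 85%):

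| Subjects × points | ICC 0 | 0.02 | 0.05 | 0.10 | 0.20 |
|---|---|---|---|---|---|
| 40 × 9 | 2.0% | 2.8% | 4.1% | 6.3% | 10.4% |
| 40 × 10–18, varying by subject (simulated) | 2.2% | 3.6% | 6.0% | 9.3% | 14.9% |
| 40 × 34 | 2.5% | 6.4% | 11.5% | 17.6% | 24.8% |
| 60 × 18 | 2.1% | 3.9% | 6.7% | 10.9% | 17.1% |

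The 34-point case is 17 × 2: the protocol has capnography for items 1–17 annotated, and the SAP does not say which items enter Analysis 1.

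**5. Away from the boundary.** At a true 83% with 40 × 18 points, simulated false success is 0.6%, 1.9% and 5.5% at ICC 0.05, 0.10 and 0.20.

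**6. Observed share needed once clustering is allowed for** (logit scale, t on 39 df): 639, 645 and 654 of 720, or 88.8%, 89.6% and 90.8%, at ICC 0.05, 0.10 and 0.20. For ICC 0.10: p = 645/720 = 0.8958; logit SE = √[2.7/(720 × 0.8958 × 0.1042)] = 0.200; 2.152 − 2.023 × 0.200 = 1.747, which back-transforms to about 85.1%, just above the threshold.

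**The case against.** The size rests on an ICC that nobody has seen. At 0.01 with nine points per subject there is essentially no inflation. The main figures also assume that any two of a subject's points are equally correlated. If only the two postures of one reading correlate, the design effect is 1 + ρ and the normal approximation gives 2.6%, 2.8%, 3.1% and 3.7% at ρ 0.02 to 0.20. They further assume one pass rate at every breathing rate. Subjects follow nearly the same set of rates, so differences between rates make a binomial interval conservative: with assumed rate-specific pass rates of 61% to 97% averaging 85%, false success is 3.1%, 5.1%, 8.6% and 13.8% at ICC 0.02 to 0.20.

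The protocol counts nine readings per subject, and the SAP's posture wording could mean separate summaries. The good-quality filter and the repeat rule, under which "the measurement must be repeated until the data quality is deemed sufficient", may also reduce correlation. The risk is concentrated in devices whose true performance is close to 85%. Finally, several clustered intervals would answer the defect, and the Bland-Altman limits and mean-error interval do not decide the endpoint.

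All of this limits the size that can be claimed, and the last two points about the remedy are accepted. None of it supports independence. Inflation remains in every case examined with a subject-level ICC of 0.02 or more, and filtering by signal quality does not show that the remaining errors are uncorrelated. A prespecified rule cannot rely on the result landing far above 85%.

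**Conclusion.** The concern holds. Independence is stated outright, lacks relevant support, and enters the one interval that decides the respiration-rate claim. For 40 subjects with 18 points each, false success at a true 85% is about 4% to 18% over assumed ICCs of 0.02 to 0.20, against a nominal 2.5%; with nine points it is about 3% to 10%. These figures depend on the ICC, the correlation structure and the number of usable points, none of which the documents settle, and they apply at the boundary. At ICC 0 there is no inflation. An observed share between 87.6% and roughly 89% to 91% is where the SAP rule and a clustered rule would disagree at ICC 0.05 to 0.20. This should be corrected before the analysis is run.

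**What to change.** **Core change (SAP Analyses 1 and 1-2).** Delete the independence statement, name the subject as the cluster, and state whether items 1–9 or 1–17 enter. Keep the requirement that the lower limit exceed 85%, but compute the interval from subject totals. With yᵢ points within ±2 out of mᵢ good-quality points for subject i, and K subjects:

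p = Σyᵢ/Σmᵢ; SE = √[K/(K−1) × Σ(yᵢ − p·mᵢ)²]/Σmᵢ.

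Form the interval on the logit scale with t on K−1 degrees of freedom (logit SE = SE/[p(1−p)]) and transform back. If every point passes, SE is zero; use the exact bound with n equal to the number of subjects (40 of 40: 0.025^(1/40) = 91.2%). Report the ICC and show the binomial interval only as a sensitivity result.

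In simulation this interval held false success at 2.1% to 3.0% over ICC 0 to 0.20 with 18 points, and at 2.2% to 2.9% with 10–18 points. A plain percentile bootstrap of subjects gave 3.1% to 4.6%, and an uncorrected robust normal interval 3.4% to 5.5%. Another prespecified clustered interval with a small-sample correction would also serve.

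**Secondary changes.** In Analysis 1-3, resample whole subjects and use repeated-measures Bland-Altman limits (between- plus within-subject variance). In Analysis 1-4, use a subject-clustered interval for the mean error. In the protocol's Sample Size Justification, state that the minimum of 23 subjects is conditional on independent readings and powers mean error, not the 85% rule.

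**Cost.** SAP wording and standard code, with no new data, but a real loss of power if readings correlate. The interval widens by √(1 + 17 × ICC): 1.16, 1.36, 1.64 and 2.10 times at ICC 0.02 to 0.20. Simulated power at an assumed true 90%, 18 points per subject:

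| Rule | ICC 0 | 0.02 | 0.05 | 0.10 | 0.20 |
|---|---|---|---|---|---|
| Binomial, 40 subjects | 98.3% | 97% | 94% | 90% | 85% |
| Clustered, 40 subjects | 97.5% | 91% | 80% | 62% | 42% |
| Clustered, 60 subjects | 99.9% | 98% | 93% | 81% | 60% |

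The binomial rule's apparent advantage at positive ICC comes with the inflated error rate above. Fixing enrolment at the protocol's ceiling of 60, before any respiration-rate results are seen, would recover much of the loss.
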